5.2.1.3 Multiplicity Control

No formal hypothesis test is planned for this pilot study. P values and confidence intervals may be provided for exploratory purposes and are unadjusted for multiplicity.

5.2.2 Primary Endpoint

5.2.2.1 Primary Efficacy Endpoint

Capture rates is evaluated daily during participant phase 1 and phase 2. Daily capture rate (%) is defined as:

captured urine weight / (captured urine weight + leaked urine weight) *100

The primary efficacy endpoint is derived by computing the mean of daily capture rate during each phase. Descriptive statistics of the primary efficacy endpoint, including mean, standard deviation, median, and range will be provided by treatment and phase. A scatter plot for Capture Rate (y axis) vs. Day # (x axis), with different colors representing PureWick and Hollister and different panels representing study subject will also be provided. The summary statistics (mean, 95% CI for mean, median) for paired difference in mean daily capture rate between the two treatment arms and p-value from Wilcoxon signed rank test or Paired t-test will be provided. Normality test will be performed before the test, if the data is normally distributed then Paired t-test will be used, otherwise Wilcoxon signed rank test will be used. Sensitivity analyses using linear mixed model (with treatment, phase, and study day as the fixed effect, and participant as the random effect), beta regression (with treatment, phase, and study day as the fixed effect, and participant as the random effect) will also be performed.

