10.0 STATISTICAL METHODS

The statistical analysis plan will be finalized prior to database lock and will include a more technical and detailed description of the statistical analyses described in the following sections. Analyses will be performed per protocol and statistical analysis plan. Any deviation from planned analyses will be described in the clinical study report along with justification of change. This section includes a summary of the planned statistical analyses of the most important endpoints including primary and key secondary endpoints.

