10.5 Primary Endpoint(s)

10.5.1 Primary Efficacy Endpoint

Capture rates is evaluated daily during participant phase 1 and phase 2. Daily capture rate is defined as:

captured urine weight / (captured urine weight + leaked urine weight)

The primary efficacy endpoint is derived by computing the mean of daily capture rate during each phase. Descriptive statistics of the primary efficacy endpoint, including mean, standard deviation, median, and range will be provided by treatment. The paired difference in mean daily capture rate between treatments will be provided.

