2.3 Randomization and Blinding

Subjects will be randomized 1:1 to the two sequences of treatment (using PureWick[™] FECs in phase 1 and Hollister® Female External Pouch in phase 2, or the reversed order). This design allows the evaluation of elements such as the carryover effect, period effect, and sequence effect. To begin treatment phase in either the U.S. or France, using a prepared randomization schedule participants will be randomized 1:1 to use either PureWick[™] FEC in phase 1 and Hollister® FUP in phase 2, or vice versa. Block randomization will be carried out using a fixed block size of 2 and stratified by investigational site and geography.

This is an open-label study. Blinding is not applicable.

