4.0 ANALYSIS POPULATION SET(S)

4.1 Populations Definitions

The following populations are defined:

Population	Description	
Enrolled	Subjects who signed ICF.	
Intent-to-Treat (ITT)	Subjects who signed ICF and randomized to a treatment sequence.	
As-Treated (AT)	ITT subjects, grouped by actual treatment sequence, if different from planned treatment sequence.	
Per-Protocol (PP)	ITT subjects without major protocol deviation.	

ITT population will be used for the analyses of endpoints. Sensitivity analyses may be carried out using AT or PP population.

Study ID: UCC-8007

Version No:

01

GFM-10082C

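### The main capture-rate comparison has no phase term, so a phase effect above about 0.055 SD of the paired differences makes its 95% CI wider than this crossover requires

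*SAP*

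**What the plan says.** For the primary efficacy endpoint, SAP 5.2.2.1 averages the daily capture rates within each phase. It then gives a mean, a 95% CI for the mean and a median for the "paired difference in mean daily capture rate between the two treatment arms and p-value from Wilcoxon signed rank test or Paired t-test". Protocol 10.5.1 likewise says "The paired difference in mean daily capture rate between treatments will be provided". Neither text has a phase or sequence term in this comparison.

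Phase appears in two other places in SAP 5.2.2.1: the descriptive statistics, which are tabulated by treatment and phase, and the "Sensitivity analyses using linear mixed model (with treatment, phase, and study day as the fixed effect, and participant as the random effect"), with a beta regression on the same terms.

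On the design, SAP 2.3 states "This design allows the evaluation of elements such as the carryover effect, period effect, and sequence effect", and on allocation "Block randomization will be carried out using a fixed block size of 2 and stratified by investigational site and geography". SAP 5.2.1.3 adds "No formal hypothesis test is planned for this pilot study"; p-values and confidence intervals are exploratory.

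**The concern.** In a 2x2 crossover, anything that changes capture rate between phase 1 and phase 2 regardless of device moves the paired differences in opposite directions in the two sequences. Pooling them counts that systematic shift as random variation. Averaging the two sequence means removes it.

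The primary objective is to compare the devices and no formal test is planned, so the device estimate and its CI carry the result. With about 30 participants, precision is worth keeping. The pilot is also meant to inform the next trial's sample size. The documents do not say which variance will be used. If it is the raw variance of the paired differences, it would be inflated by a factor of about 1 + p²/s², that is by about 11% at p/s = 1/3 and 44% at p/s = 2/3.

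**Working it through.** **Inputs from the documents.** About 30 participants, 1:1 to two sequences, blocks of 2 by site (SAP 2.3, 2.4). About four sites (Protocol synopsis) or two (Protocol 4.1).

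**Assumed, because the documents give no value.** Within-sequence SD of the paired differences s = 15 or 20 points; phase effect p (phase 2 minus phase 1) = 5, 10 or 15 points; n = 30 with both phases. There is no stated figure in the plan to reproduce.

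**1. Mean and variance.** With device difference τ (PureWick minus Hollister), the expected difference is τ − p for PureWick first and τ + p for Hollister first.
- Bias of the pooled mean, in size: p·|n1 − n2|/n
- Pooled variance of the differences: about s² + p²·4·n1·n2/n²

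**2. CI half-widths at 15/15.**
- Planned: t(29)·√(s² + p²·30/29)/√30, with t(29) = 2.0452
- Phase-adjusted: t(28)·s/√30, with t(28) = 2.0484

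| s | p | planned | adjusted | ratio | simulated coverage, planned |
|---|---|---|---|---|---|
| 15 | 5 | 5.91 | 5.61 | 1.05 | 96.2% |
| 15 | 10 | 6.77 | 5.61 | 1.21 | 98.2% |
| 15 | 15 | 7.99 | 5.61 | 1.42 | 99.4% |
| 20 | 5 | 7.71 | 7.48 | 1.03 | 95.6% |
| 20 | 10 | 8.38 | 7.48 | 1.12 | 97.1% |
| 20 | 15 | 9.39 | 7.48 | 1.26 | 98.6% |

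Coverage comes from 100,000 simulated trials per case with normal differences. The phase-adjusted interval covered 94.9-95.2% in every case.

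**3. Break-even.** The lost degree of freedom costs 2.0484/2.0452 = 1.0016. At 15/15 the two widths are equal at p/s = √((1.00155² − 1)·29/30) = 0.055, which is 0.8 points at s = 15 and 1.1 at s = 20. At 17/13 the adjusted width also carries √(30·(1/17 + 1/13)/4) = 1.009, a total of 1.011, and break-even rises to about 0.14.

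**4. Unequal sequences.** Blocks of 2 leave an imbalance of at most one per site, so at most 17/13 with four sites or 16/14 with two.
- Bias for p = 5, 10, 15: 0.3, 0.7, 1.0 points at 16/14 and 0.7, 1.3, 2.0 at 17/13. Coverage of the planned CI at these splits was 95.5-99.1%.
- At an analysed split of 14/8, coverage was 94.5, 93.3, 93.4% (s = 15) and 94.8, 93.8, 93.3% (s = 20).

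The 17/13 limit applies at randomisation, not at analysis. The allocation envelope is opened once eligibility is confirmed (Protocol 7.2.4), but a skin score above 0 at the later baseline visit can still end in no treatment (7.2.6). A phase can also be stopped early (7.2.7, 10.6.4). An early stop still yields a phase mean from the available nights (SAP 5.2.1.1), so the pair is lost only if one phase has no evaluable night.

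**5. The planned mixed model.** Study day is a fixed effect, which implies nightly records; participant is the only random effect. Let night-to-night SD be e, with 28 nights per phase. The participant-by-phase variance is then g = s²/2 − e²/28. Left out of the model, about half of g (0.51g) goes into the residual, and the model's SE is about √(2(e² + 0.51g)/(28·30)). The correct SE is s/√30.
- s = 15, e = 10: g = 108.9; model SE 0.61 against 2.74; coverage about 33%.
- s = 15, e = 30: g = 80.4; 1.50 against 2.74; about 72%.
- s = 10, e = 30: g = 17.9; 1.47 against 1.83; about 89%.
- s = 8, e = 30: g ≈ 0; 1.46 against 1.46; about 95%.

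**The case against.** The strongest reply is that nothing planned here is invalid. At every split that randomisation allows, the planned CI covered at least 95% in the cases tried. No margin, acceptance criterion or decision depends on its width. The paired difference is the protocol's own summary, so the SAP follows the protocol. All of this stands, and it keeps the priority low.

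The loss is also hypothetical. The documents give no reason to expect a phase effect of 10 to 15 points. Training is repeated in each phase, and phase 2 starts only after washout, re-screening and a skin score of 0. This stands in part. Those steps limit carryover and differences in starting skin condition, but they do not rule out a change over time that affects both devices.

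Phase is not ignored either. In participants with both phases, the treatment-by-phase means yield the phase-adjusted point estimate by hand. They do not yield its standard error, and no planned analysis is specified to give a valid phase-adjusted interval.

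A reader might infer that the mixed model's interval must be far too narrow. The documents do not support that. The SAP states no covariance structure, and the result depends on variances it does not give: coverage is close to 95% when night-to-night noise explains the whole spread of the paired differences.

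**Conclusion.** The point holds as a matter of efficiency. If the phase effect exceeds about 0.055 of the within-sequence SD (15/15; more with unequal sequences), the main CI is wider than the design requires. Under the assumed SD of 15-20 points, the widening is about 3-5% at p = 5, 12-21% at p = 10 and 26-42% at p = 15. The actual widening cannot be stated, because the documents give neither the SD nor a phase effect.

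Three stronger readings go too far:
- That any phase effect widens the CI: below the break-even the saved degree of freedom outweighs it, by less than 0.2% of width at 15/15.
- That the device estimate is materially biased or its CI misleading: bias is small and the CI conservative at near-balanced splits, and even 14/8 gives only mild under-coverage, about 93-95%.
- That blocks of 2 guarantee near balance in the analysis: they limit only the randomised split.

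The mixed model as written does not reliably fill the gap. If fitted to nightly records without a participant-by-phase term, its interval is too narrow whenever device response varies between participants; coverage runs from about 30% to 95% under the SDs tried. In an exploratory pilot, this is a cheap improvement of optional-to-should priority.

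**What to change.** In SAP 5.2.2.1, make the main device estimate and 95% CI phase-adjusted on participant phase means, among participants with both phases. Use the average of the two sequence means of the paired differences, with the pooled within-sequence variance and n − 2 degrees of freedom. Equivalently, fit treatment and phase as fixed effects and participant as random to those phase means.

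SAP 4.1 says "ITT population will be used for the analyses of endpoints". A paired difference exists only for participants with both phases, so the adjusted analysis uses the same people as the planned one.

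Keep the unadjusted paired difference of Protocol 10.5.1 as a supportive summary. Record the change, since Protocol 10.0 requires that "Any deviation from planned analyses will be described in the clinical study report along with justification of change".

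If the nightly mixed model stays as a sensitivity analysis, state its covariance structure and include a participant-by-phase term.

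The cost is SAP wording, a note in the study report and one degree of freedom. If there is no phase effect, the CI is 0.2% wider at 15/15 and 1.1% wider at 17/13. No new data or visits are needed.

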2.4 Sample Size

Approximately 30 participants will be enrolled. The sample size is planned based on operational and practical considerations and is adequate for the purpose of this pilot study.

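### The capture-rate p-value switches between paired t and Wilcoxon on an unspecified normality pre-test while the interval stays on the mean, so with skewed differences the two can disagree

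*SAP*

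**What the plan says.** All of this is in SAP 5.2.2.1 unless stated otherwise.

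- **Endpoint.** "The primary efficacy endpoint is derived by computing the mean of daily capture rate during each phase". Each woman therefore contributes one mean per device.
- **Estimate and interval.** The plan promises "The summary statistics (mean, 95% CI for mean, median) for paired difference in mean daily capture rate between the two treatment arms". The interval is for the mean whichever test is chosen. The median has no interval, and no Hodges-Lehmann estimate is planned.
- **P-value.** "Normality test will be performed before the test", and then "if the data is normally distributed then Paired t-test will be used, otherwise Wilcoxon signed rank test will be used".
- **Sensitivity analyses.** A linear mixed model and a beta regression, each with treatment, phase and study day as fixed effects and participant as random effect, are run regardless of the normality result.
- **Status.** SAP 5.2.1.3 says "No formal hypothesis test is planned for this pilot study" and labels p-values and intervals exploratory and unadjusted; SAP 1.2 also rules out a formal test.
- **Size.** SAP 2.4: "Approximately 30 participants will be enrolled", on operational grounds, with no SD, effect size or dropout rate.

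Protocol 10.5.1 asks only for descriptive statistics by treatment and the paired difference. The switching rule is an addition made in the SAP.

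**The concern.** The endpoint and the interval concern a mean. The signed-rank test does not test a mean: its null hypothesis is that the differences are symmetric about zero, and the matching estimate is the Hodges-Lehmann pseudo-median. With symmetric differences the two centres coincide. With skewed differences they separate.

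Skew is a plausible way to fail the pre-test here. Capture rate cannot exceed 100%, so a device that fits most women well but leaks heavily in a few gives differences with one long tail. The rule then leaves the t-test because of skew and moves to a test that reads as a test of location only without skew.

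The report could then show a significant p-value for a device whose mean capture is no better, beside an interval for the mean that includes zero. The reverse can also happen. Because the pre-test is not specified, the choice of test is also not fixed in advance.

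**Working it through.** **Inputs.** From the SAP: the switching rule, the interval for the mean, and about 30 participants, hence at most about 30 pairs. Assumed, because the documents are silent: Shapiro-Wilk at 5% on the paired differences; two-sided 0.05 to match the 95% CI; 24 pairs as an example of some loss; every distribution below. The plan states no figure to reproduce.

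**Step 1: a 30-pair example.** Differences are device A minus device B in percentage points. Let 26 women lie evenly from +1 to +4 and four lie at −20, −25, −30 and −35.

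- Mean = (26 × 2.5 − 110)/30 = −45/30 = −1.50.
- Sum of squares = 183.56 + 3150 = 3333.56. Variance = (3333.56 − 30 × 1.50²)/29 = 112.6, so SD = 10.61 and SE = 10.61/√30 = 1.94.
- 95% CI = −1.50 ± 2.045 × 1.94 = −5.46 to 2.46; paired t p = 0.445.
- Shapiro-Wilk p = 6 × 10⁻⁹, so the rule selects Wilcoxon.
- W+ = 26 × 27/2 = 351 and W− = 27 + 28 + 29 + 30 = 114. The null mean is 465/2 = 232.5 and the null SD is √(30 × 31 × 61/24) = 48.6, so z = 118.5/48.6 = 2.44. The computed p is 0.014, favouring A.

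The report would print p = 0.014 in favour of A (median +2.26) beside a mean of −1.50 with an interval that includes zero.

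**Step 2: the reverse.** Let 23 women lie evenly from +1 to +4 and seven from −25 to −55 in steps of 5. Mean = (57.5 − 280)/30 = −7.42, 95% CI −14.49 to −0.34, t p = 0.041. W+ = 276 and W− = 189, so the reported Wilcoxon p = 0.38. The interval excludes zero and the p-value is far from significant.

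**Step 3: how often, with failures on one device only.** Both devices have true mean capture 85%. Device A is Beta(51, 9). On device B a fraction q of women average f, and the rest average (0.85 − qf)/(1 − q):

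- q = 10%, f = 0.50: rest 0.889
- q = 15%, f = 0.45: rest 0.921
- q = 20%, f = 0.60: rest 0.913

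Ranges across these scenarios and several independent runs (3,000 to 8,000 trials each, with slightly different assumed spreads):

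| Pairs | Rule gives p < 0.05 | Paired t gives p < 0.05 | p and CI disagree on significance |
|---|---|---|---|
| 24 | 18–44% | 7–12% | 13–37% |
| 30 | 24–49% | 7–8% | 19–42% |

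About 99% or more of the significant results favour the device that fails in some women.

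**Step 4: other shapes.**

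- Same failure mixture on both devices, 24 and 30 pairs: rule 4–5.5%, t-test 4–6%, disagreement 2–5%.
- Device B failing 1.5 times as often as A: rule 11–15%, disagreement 8–13%.
- Both devices Beta(8.5, 1.5): disagreement about 0.5%.
- Normal differences: disagreement 0.1–0.3%.
- A harsher family, simulating differences directly with 10–20% of women near −20 to −30 points and the rest near +3, true mean 0 to −3.6: at 30 pairs, disagreement 34–65%, and a significant Wilcoxon pointing away from the observed mean in 4–20%. At 20 pairs these are 21–43% and 1–7%.

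**Step 5: effect of the fix.** With the p-value taken from the paired t-test, p and interval agree by construction: p = 0.445 with −5.46 to 2.46 in step 1, and p = 0.041 with −14.49 to −0.34 in step 2.

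**The case against.** Four points can be made for the plan.

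1. **This is not the only comparative analysis.** A reader might infer that the switching p-value is the sole test of the device effect. It is not: the mixed model and beta regression both carry a treatment term and ignore the pre-test. This stands. They are sensitivity analyses, however, and do not repair a headline line whose p-value and interval conflict.

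2. **The p-values are exploratory.** No decision rule uses p < 0.05. A reader might also infer that this p-value drives reimbursement or the next trial's sample size. SAP 1.1 says only that the study data will aid reimbursement and that the pilot will inform sample size; a sample size would come from the mean difference and SD, which this rule does not touch. This stands and limits the severity.

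3. **The pattern would be visible.** The mean, interval, median, range and per-subject plots would show a few severe failures. This largely stands, but it leaves readers to resolve a conflict that the plan need not create.

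4. **A ceiling on each rate does not imply skewed differences.** If both devices fail in some women, the differences are roughly symmetric with heavy tails, a case the signed-rank test suits. This stands, and it is why the size runs from near zero upward.

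Two further inferences go too far. The 18–49% in step 3 is not a false-positive rate under identical devices: there, most women truly do slightly better on device B, and Wilcoxon detects that. It answers a different question; it is not an invalid test. Nor do p and CI contradict each other in the strongest sense: a significant Wilcoxon with an interval excluding zero on the opposite side occurred in none of the direct-difference simulations (3,000 runs per scenario).

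**Conclusion.** The concern holds as a modest, easily corrected flaw in the headline efficacy comparison. The plan pairs an interval for the mean with a p-value that may concern another quantity, and leaves the choice to an unspecified pre-test. With skewed differences the two can disagree on significance, or the p-value can point away from the mean.

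The size depends on shape. Disagreement is about 13–42% of trials with one-sided failures, equal beta-distributed means and 24 to 30 pairs, and higher under the harsher mixtures. It is about 2–5% if both devices fail similarly and under 1% if differences are near normal. These figures assume Shapiro-Wilk at 5% and a two-sided 0.05 level. The documents give no SD or shape for capture rate, so they cannot say which case applies. They do not support a claim that the study's efficacy conclusion rests on this p-value alone.

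**What to change.** In SAP 5.2.2.1, delete the normality pre-test and the choice of test that follows from it. Replace them with two statements:

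- The mean paired difference in mean daily capture rate is always reported with its paired-t 95% CI and the p-value from that same analysis.
- The Hodges-Lehmann estimate with its Wilcoxon-based 95% CI and p-value is always reported as a separately labelled sensitivity analysis of a different quantity.

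This costs two sentences and one extra table row. It needs no new data and conflicts with nothing in Protocol 10.5.1. If the analysis has already been run, Protocol 10.0 requires the change to be described and justified in the clinical study report. The downside is that the paired t-test remains mildly liberal under strong skew (about 7–12% against a nominal 5% in the assumed one-sided scenarios), which is why the second row should appear every time.

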10.4.2 Poolability of Data

The effect of investigational site will be evaluated using regression models, with primary endpoint as the dependent variable, and treatment, investigational site, and the interaction term between treatment and investigational site as fixed effects.

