5.0 STATISTICAL ANALYSIS / CALCULATIONS

5.1 Derived Variables

Daily capture rate (%) is defined as: captured urine weight / (captured urine weight + leaked urine weight) *100, where

- Captured urine weight is defined as:
 - PureWick(TM): Canister final weight (g) Canister starting weight (g), and
 - Hollister(R): Graduated cylinder final weight (g) Graduated cylinder baseline weight (g)
- Leaked urine weight is defined as:
 - bed pad 1 post-use weight (g) bed pad 1 pre-use weight (g) when the answer for "Was 2nd bed pad used?" is equal to "No" on Case Report Form (CRF) page PureWick(TM) Participant Placement or Hollister(R) Female External Collection Pouch Participant Placement and OR
 - (pad 1 post-use weight (g) bed pad 1 pre-use weight (g)) +(pad 2 post-use weight (g) bed pad 2 pre-use weight (g)) when the answer for "Was 2nd bed pad used?" is equal to "Yes" on Case Report Form (CRF) page PureWick(TM) Participant Placement or Hollister(R) Female External Collection Pouch Participant Placement
 - OR
 - (pad 1 post-use weight (g) bed pad 1 pre-use weight (g)) +(pad 2 post-use weight (g) bed pad 2 pre-use weight (g)) +(Mesh underwear post-use weight (g) Mesh underwear pre-use weight (g) when theDaily answer for "Was 2nd bed pad used?" is equal to "Yes" and when the answer for "Did participant use the mesh underwear provided while using the study device?" is equal to "Yes"(This scenario only applies to PureWick™ group.).
 - o OR
 - (pad 1 post-use weight (g) bed pad 1 pre-use weight (g)) +(Mesh underwear post-use weight (g) Mesh underwear pre-use weight (g) when the answer for "Was 2nd bed pad used?" is equal to "No" and when the answer for "Did participant use the mesh underwear provided while using the study device?" is equal to "Yes" (This scenario only applies to PureWick™ group.).

A void of which (captured urine weight + leaked urine weight) < 10 g is considered not evaluable for the purpose of analyzing capture rate.

- 5.2 Analysis Methods
 - 5.2.1 General Considerations
 - 5.2.1.1 Handling of Missing Data

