5.2.1.2 Poolability of Data

The effect of investigational site will be evaluated using regression models, with primary endpoint as the dependent variable, and treatment, investigational site, and the interaction term between treatment and investigational site as fixed effects.

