The questionnaire will be completed on Day 1, Day 15 and Day 29 of both study phases. We will categorize the questionnaire timepoint as baseline, week 1-2 (day 2-17) and week 3-4 (> day 17), respectively. If day 15 is missing, the latest record between day 2 and 17 will be used for week 1-2; if day 29 is missing, the latest record after day 17 will be used for week 3-4. Descriptive statistics will be provided by each questionnaire timepoint, treatment, and phase. A scatter plot for N-QoL (y axis) vs. Day # (x axis), with different colors representing PureWick and Hollister and different panels representing study subject will also be provided. Linear mixed model may be used, with treatment, phase, and day number as the fixed effect, and participant as the random effect.

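### The nightly capture-rate sensitivity models have participant as their only random effect, so the device interval is too narrow if a participant's two phases differ; the poolability model names no participant term (minor; the paired main analysis is unaffected)

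*SAP*

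**What the plan says.** The main efficacy analysis reduces each participant to one mean capture rate per phase and reports "The summary statistics (mean, 95% CI for mean, median) for paired difference in mean daily capture rate between the two treatment arms", with a paired t-test or a Wilcoxon signed rank test (SAP 5.2.2.1).

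The same section then commits to two further models: "Sensitivity analyses using linear mixed model (with treatment, phase, and study day as the fixed effect, and participant as the random effect") and "beta regression (with treatment, phase, and study day as the fixed effect, and participant as the random effect) will also be performed". Because study day is a covariate, both run on nightly records, up to 28 per participant per phase (Protocol 4.1). No participant-by-phase effect and no within-phase correlation structure is named.

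Three other places bear on the point:

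- The optional N-QoL model in SAP 5.2.3.1 has the same structure: "Linear mixed model may be used, with treatment, phase, and day number as the fixed effect, and participant as the random effect".
- For poolability, Protocol 10.4.2 says "The effect of investigational site will be evaluated using regression models, with primary endpoint as the dependent variable", and SAP 5.2.1.2 lists "treatment, investigational site, and the interaction term between treatment and investigational site as fixed effects". Neither names a participant term.
- SAP 5.1 sets the only evaluability rule for capture rate: "A void of which (captured urine weight + leaked urine weight) < 10 g is considered not evaluable". No rule for nights at exactly 0% or 100% appears in the text supplied. Appendix 2 of the SAP (derived data specification) is listed but was not available.

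**The concern.** In a two-period crossover the device is assigned to a participant's phase, not to a night. Variation specific to one participant in one phase, such as fit or placement technique that persists for four weeks, does not average out over nights. A model with only a participant effect treats that variation as independent nightly error and divides it by the number of nights. Positive correlation between adjacent nights has the same effect. Common treatment and phase effects are already fitted as fixed effects, so the question is only about variation beyond them.

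These two models are the only planned device estimates for capture rate that adjust for phase, and they are there to support the paired result. As written they can look more precise than that result for no real reason.

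The poolability model has a different problem. With two phase means per participant and no participant term, the site comparison counts each participant twice. The treatment-by-site comparison, which is within participants, is charged with between-participant variance.

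The beta model has one more gap. A night with no pad gain is exactly 100% and a night with nothing captured is exactly 0%. Either is evaluable if the total is at least 10 g, and neither can enter a beta likelihood.

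**Working it through.** The plan gives no variance, effect size or power for these models, so there is no figure of its own to reproduce. Inputs from the documents are 30 participants (Protocol 10.2, SAP 2.4), m = 28 nights per phase (Protocol 4.1), and 2 sites (Protocol 4.1) or 4 sites (2 in France plus 2 in the U.S., Protocol synopsis). All variance inputs below are assumptions.

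**Nightly linear model, phase-level variance.** Set within-participant variance to 1, with share s at participant-by-phase level and 1 − s at night level, and n = 30.

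- True variance of the device difference: 2[s + (1 − s)/m]/n.
- Variance the participant-only model reports: 2·{[(2m − 1)(1 − s) + m·s]/(2m − 1)}/(m·n).

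At s = 0.10:

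- True variance: 2(0.10 + 0.90/28)/30 = 0.00881, SE 0.0939.
- Reported variance: 2 × [(55 × 0.90 + 28 × 0.10)/55]/(28 × 30) = 2 × 0.9509/840 = 0.00226, SE 0.0476.
- Ratio: 0.0939/0.0476 = 1.97.
- Rejection with no device effect: 2·P(Z > 1.96/1.97) = 32%.

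| Share s | True SE / reported SE | Nominal 5% test rejects | 95% interval covers |
|---|---|---|---|
| 0 | 1.00 | 5% | 95% |
| 2% | 1.25 | 12% | 88% |
| 5% | 1.55 | 21% | 79% |
| 10% | 1.97 | 32% | 68% |
| 20% | 2.66 | 46% | 54% |

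Simulation (6,000 trials per share, with treatment, phase and day fitted) gave ratios 1.01/1.24/1.54/1.95/2.68. In those trials the paired test rejected 4.6 to 5.4% and participant-clustered errors 5.0 to 5.8%. At s = 10% a separate simulation gave mean 95% interval widths of 0.19 for the participant-only model and 0.38 for the paired t. No size was computed for the beta model.

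**Nightly linear model, correlation between adjacent nights only.** For first-order autocorrelation r, the variance of a 28-night mean is inflated by v = (1 + r)/(1 − r) − 2r/[28(1 − r)²], and the SE ratio is √{v/[(56 − v)/55]}.

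- r = 0.2: v = 1.478, ratio 1.22.
- r = 0.4: v = 2.254, ratio 1.52.

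**N-QoL model, if it is run.** The same formulas apply with few records per phase. At s = 5/10/20/40% the ratio is 1.03/1.07/1.13/1.27 with 2 records and 1.06/1.12/1.23/1.46 with 3.

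**Poolability model, run as ordinary regression on phase means.** Let the within-participant correlation be 0.3/0.5/0.7. Results are from 40,000 simulated trials per setting, at a nominal 5%.

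| False rejection | 2 sites | 4 sites |
|---|---|---|
| Site | 8.6/11.0/13.4% | 10.8/15.1/19.4% |
| Treatment by site | 2.03/0.76/0.07% | 1.40/0.24/0.01% |

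With participant in the model, and phase for the interaction, all of these are 4.8 to 5.2%.

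For power, suppose the device effect differs by 1 SD between 2 sites of 15. The true SE of that contrast is √[4(1 − r)/15], here with r the within-participant correlation: 0.432/0.365/0.283. The ordinary regression uses about √(4/15) = 0.516 whatever the correlation. Power is 48/47/46% as written. With participant and phase in the model (27 df), it is 61/75/93%.

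**Beta boundary.** The beta log-density is minus infinity at 0 or 1 (checked at shape parameters 8 and 2), so a single such night stops an ordinary beta fit unless a rule is applied.

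**The case against.** Little turns on these models. The SAP states "No formal hypothesis test is planned for this pilot study", its p-values and intervals are exploratory, and no poolability threshold is set. The paired difference and its interval are reported alongside, so an implausibly narrow nightly interval would be visible. No bias in the device estimate is shown. Blocks of 2 by site (SAP 2.3) keep the sequences nearly balanced, so the paired mean is already close to phase-adjusted. All of this stands, and it is why the point is rated minor.

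The sizes rest on assumed variance shares, and with a zero share and independent nights the model is correct. That also stands: the direction is firm and the size is not.

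The poolability text lists fixed effects only, so a participant random effect is unstated rather than ruled out. This is fair. The figures above apply only if the model is run as ordinary regression with the terms listed. The fair request is that the participant term be stated.

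Appendix 2 may already contain a rule for 0% and 100% nights. This too is fair, and that part is a query rather than an established defect. The N-QoL effect is small and its model optional.

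None of this answers the main point. Both nightly models are committed to, and the text gives neither of them a term for variation between a participant's phases.

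**Conclusion.** The concern holds, at minor severity. As specified, the two nightly capture-rate models understate the uncertainty of the device effect whenever there is participant-by-phase variance or positive night-to-night correlation. For the linear model at 30 participants and 28 nights, a 2% phase-level share already brings 95% coverage down to about 88%, and a 10% share to about 68%. No size is claimed for the beta model.

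The poolability model, if run with only the listed terms, errs in both directions: too many site differences, and too little power for the interaction, which is the more important poolability question.

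The harm is limited to exploratory intervals and p-values. The paired estimate, its interval and the descriptive SDs do not change.

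**What to change.** - **Nightly models.** Add a participant-by-phase random effect to the linear mixed and beta models, and to the N-QoL model if it is run. Name participant-clustered robust standard errors as the fallback if a fit fails.
- **Poolability.** State participant as a random effect and phase as a fixed effect in the model.
- **0% and 100% nights.** State the rule before database lock, or point to it if Appendix 2 already has one. A fractional logit with participant-clustered errors and a zero-one-inflated beta model are two options. The second is heavier and may not converge with about 30 participants.

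The first two changes are a few lines of SAP wording and SAS code. The third is a sentence of SAP text, plus a change of model if one of these options is chosen. None needs new data, visits or participants. The nightly-model intervals will generally be wider and the site effect less precise, while the interaction estimate becomes more precise.
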